The effect of gluten-free diet on type 1 diabetes (T1D)

NCT02867436

January 10th, 2016

Trial design

This study is a prospective non-randomized intervention trial.

Participants

Study participants were recruited from children patients diagnosed with T1D at inpatient pediatric diabetes clinics at two centers in Prague, Czech Republic (University Hospital Prague-Motol and University Hospital Prague-Královské Vinohrady). Both centers are tertiary care hospitals that annually admit over 65 children patients with newly diagnosed T1D. The recruitment will last from January 2016 to January 2018. Subjects and their parents have the right to withdraw from the study at any time without giving the reason.

Eligibility criteria

Following inclusion criteria will be applied:

- T1D diagnosed according to the ADA criteria [1]
- age 4 – 17.99 years at onset
- positivity of a least one T1D associated antibody (IAA, anti-IA2, anti GAD65)
- presence of high risk HLA-DQB1*03:02-DQA1*03 or DQB1*02-DQA1*05 molecules
- no coeliac disease and negativity of anti-tissue transglutaminase antibodies
- body mass index below +2SD of the age and height standard
- no concomitant disease potentially influencing immune response or gluten sensitivity

Intervention

Subjects in the intervention group will follow strict gluten-free diet while receiving the recommended daily doses of macronutrients. Their meal records for three days prior to the visit will be required for each visit as well as a consultation with nutrition specialist. Adherence to the diet will be tested via the negativity of the gluten immunogenic peptide (GIP) in the commercial iVylisa GIP-S (Biomedal, S.L., Sevilla, Spain) ELISA kit. Stool samples will be tested for GIP presence every 3 months without especially notifying the subjects. Subjects in the intervention arm will receive financial reimbursement for the added cost of gluten-free edibles.

Study procedure

The caregivers of the subjects will sign a written informed consent with the study protocol prior to the enrollment in the first 30 days after T1D diagnosis.

All subjects will be hospitalized at T1D onset. During the hospitalization, a blood sample will be taken for the measurement of anti-GAD65, anti-IA2 and IAA, glycosylated hemoglobin (HbA1c) (performed by high liquid chromatography) and screening for coeliac disease (total IgA to rule out IgA deficiency anti anti-tissue transglutaminase antibodies analyzed by ELISA test). A stool sample will also be taken for further analysis of their gut microbiome content.

If the subjects fulfill the inclusion criteria, they will be offered to join the trial. The subjects and their parents will choose their study group freely and a mixed-meal tolerance test (MMTT) will be scheduled between 4-8 weeks after T1D onset.

The MMTT is considered a gold standard for the measurement of the endogenous production of residual insulin in subjects with T1D [2]. MMTTs will be performed for all subjects at group allocation and at 6 and 12 months. All subjects will receive a standard liquid meal Ensure Plus (Abbott Laboratories BV, Zwolle, Netherlands) and their C-peptide levels will be measured at the baseline and each 30 minutes up to 150 minutes. All MMTTs will be performed after overnight fasting and children will receive only their evening dose of long-acting insulin analogue. The MMTT will be rescheduled if the subjects' capillary glucose is <3.9 mmol/L (<70 mg/dL) or >10 mmol/L (>180 mg/dL). Serums of subjects from the second center will be transported at $4-8^{\circ}\text{C}$ within 48 hours to the central laboratory. Immediately after the first MMTT, subjects who will choose the intervention group will start with strict gluten-free diet. After the third MMTT at 12 months, subjects and their parents will be allowed to discontinue the diet at their will.

Subjects will be followed up at 3 months intervals. During each visit subjects will undergo a physical examination and their body weight, height and BMI will be measured. Their HbA1c will be measured and their total daily insulin dose noted.

Stool samples will be taken at T1D onset, allocation visit and each 3 months up to 15 months for microbiome analysis and adherence test if the patient belongs to the intervention group. The stool samples will be kept at -80°C until the DNA extraction using the PowerSoil DNA isolation kit (Qiagen, Hilden, Germany). Microbiome profiles will be determined by next-generation sequencing of the V4 variable region of 16S rDNA and processed in a bioinformatic pipeline as described previously [3].

Blood samples for the measurement of regulatory cell subsets (measured by flow cytometry) and their cytokine profiles (after short term PMA-ionsomycin re-stimulation) will be taken at baseline and at 6 and 12 months.

Intestinal permeability will be measured through serum zonulin (a marker for dysfunctional gut barrier function) levels at baseline and at 12 months [4]. In addition, urine lactulose/mannitol ratio following the ingestion of lactulose/mannitol solution (mannitol g, lactulose g in 100ml water for injection) and 6 hours urine collection [5] will be performed at 12 months (measured using high-performance liquid chromatography).

End points

Primary

- Area under the curve (AUC) of the C-peptide level during the mixed meal tolerance tests

Secondary

- HbA1c
- Insulin requirement (IU/kg)
- Insulin dose adjusted HbA1c (IDAA1c)
- Gut microbiome composition
- Immune parameters (regulatory cell subsets, cytokine production)
- Intestinal permeability (zonulin concentration and lactulose/mannitol urine excretion ratio)

Data collection nad management

All participants will be assigned a study identification number. The forms with patient data will be stored in a locked room with access only to the team of researchers at both centers. Electronic version of data will be kept in password protected databases in accordance with the GDPR legislature.

Statistical analysis

The analysis of the primary outcome will be based on an ANCOVA model with C-peptide AUC at 12 months as a response and the intervention assignment, baseline C-peptide AUC at visit 1, age, gender and body weight as covariates. The tests and confidence intervals will use robust sandwich variance estimator. The primary analysis will follow the per-protocol principle. Secondly, the results at 6 months will also be analyzed. Analyses of secondary outcomes (HbA1c, insulin dose, immune parameters and gut microbiome composition) will proceed by similar methodology. Longitudinal analyses will be performed by linear generalized estimating equation models with a working independence structure. Linear trends in continuous outcomes

over 12 months will be estimated by the intervention arm and compared with adjustment for sex, age, and baseline body weight SDS.

Ethics and dissemination

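### Insulin delivery mode and glucose-sensor use are not among the listed visit data or covariates, so a difference in device use between self-chosen arms would be read as a diet effect on the three glycaemic secondary endpoints

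*Combined protocol and SAP*

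**What the plan says.** All references are to the combined protocol and SAP.

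- **Allocation.** Trial design states "This study is a prospective non-randomized intervention trial". Study procedure adds "The subjects and their parents will choose their study group freely".
- **Burden of the diet arm.** Under Intervention, besides the strict diet: "Their meal records for three days prior to the visit will be required for each visit as well as a consultation with nutrition specialist".
- **Visit content.** Under Study procedure, follow-up is three-monthly, and each visit includes an examination with anthropometry (weight, height, BMI). On glycaemic management the section says "Their HbA1c will be measured and their total daily insulin dose noted". Stool samples are also collected.
- **Insulin regimen.** The only detail is the condition set for the mixed-meal tolerance tests (MMTTs) in Study procedure: "children will receive only their evening dose of long-acting insulin analogue".
- **Endpoints.** HbA1c, insulin requirement per kg and IDAA1c are three of the six secondary endpoints (End points).
- **Models.** Under Statistical analysis, the primary ANCOVA adjusts for C-peptide AUC at the first visit, age, gender and weight. Secondary outcomes are to be handled in a similar way. HbA1c and insulin dose are named there; IDAA1c is not, and I assume the same approach applies to it. The longitudinal models adjust for sex, age and weight SDS at baseline.

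Pump, glucose sensor and mode of delivery do not appear anywhere in the document, whether as eligibility criterion, standardised care, visit item or covariate.

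**The concern.** When families pick their arm, chance does not balance other aspects of care. A co-intervention that acts on the outcome has to be standardised, or measured and examined. Insulin pumps and glucose sensors can plausibly act on HbA1c and on insulin dose, and therefore on IDAA1c, which combines the two. Families willing to take on a strict diet with food records and extra consultations may also differ in how readily they take up devices. The documents are silent on whether they do.

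If uptake differs, the arm coefficient for these three endpoints carries the device effect along with any diet effect. None of the listed covariates stands in for device use, and the listed visit data would not let a reader see whether the arms were alike. What is at stake is the interpretation of half of the secondary endpoints.

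**Working it through.** **Inputs.** The document states no sample size, SD, alpha, effect size or device-uptake figure, so there is no figure of the plan's own to reproduce. Every input below is an assumption:

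- difference in device uptake between arms (d): 0, 20 or 40 percentage points
- device effect on the outcome (e): 0.3 to 0.5 SD
- residual SD after covariate adjustment: 0.75, in units of the outcome SD
- analysed children per arm (n): 30 to 50
- two-sided 5% test, normal approximation, true diet effect zero

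**Step 1: false difference.** With device use left out of the model and not predicted by the covariates, bias = d × e.

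- d = 0: bias 0
- d = 0.20: 0.20 × 0.3 = 0.06 SD to 0.20 × 0.5 = 0.10 SD
- d = 0.40: 0.40 × 0.3 = 0.12 SD to 0.40 × 0.5 = 0.20 SD

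**Step 2: standard error.** SE = 0.75 × √(2/n).

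- n = 30: 0.194
- n = 50: 0.150

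**Step 3: rejection rate with no diet effect.** With r = bias/SE, the rate is P(Z > 1.96 − r) + P(Z < −1.96 − r).

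| Bias (SD) | r, n = 30 | Rejects | r, n = 50 | Rejects |
|---|---|---|---|---|
| 0 | 0 | 5.0% | 0 | 5.0% |
| 0.06 | 0.31 | 6.1% | 0.40 | 6.9% |
| 0.10 | 0.52 | 8.1% | 0.67 | 10.2% |
| 0.12 | 0.62 | 9.5% | 0.80 | 12.6% |
| 0.20 | 1.03 | 17.8% | 1.33 | 26.6% |

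A gap in the other direction gives the same rates with the sign of the false effect reversed.

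**Step 4: check on the HbA1c scale.** Assuming instead that devices lower HbA1c by 2 to 6 mmol/mol, the same product gives 0 at equal uptake, 0.4 to 1.2 mmol/mol at 20 points and 0.8 to 2.4 mmol/mol at 40 points.

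A simulated ANCOVA used arm, a baseline value, age, sex and weight, with robust variance, a device effect of 4 mmol/mol and no diet effect. It had 400,000 simulated children, so that bias rather than sampling noise was seen.

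| Uptake gap | Arm estimate, planned type of covariates | Arm estimate, device indicator added |
|---|---|---|
| 0 points | 0.00 | −0.01 |
| 20 points | −0.80 | −0.02 |
| 40 points | −1.59 | −0.01 |

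The first estimates match 0.20 × 4 = 0.8 and 0.40 × 4 = 1.6. The recovery in the last column holds because uptake in the simulation depended only on arm and shared no unmeasured cause with the outcome. It shows the mechanism and does not guarantee that adjustment would work as well in the trial.

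**The case against.** **No evidence of a gap.** Nothing in the document shows that any participant used a pump or sensor, or that uptake would differ by arm. The evening long-acting dose prescribed for the MMTTs suggests injection therapy at those times. This stands as a limit on size: equal uptake means zero bias, and the low end of the non-zero range (6.1% against 5%) is trivial. It does not remove the point. The MMTT condition does not exclude pumps and says nothing about sensors, and the listed data would not let the sponsor show that uptake was equal.

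**One effect size for three endpoints.** The calculation applies a single SD effect to HbA1c, dose and IDAA1c, although devices need not move all three equally or in the same direction. This stands; the figures are an illustration and not a forecast for any one endpoint.

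**The wording can easily go too far.** Visits also record an examination and anthropometry, the case report forms are not reproduced, and clinic records may hold device data. So the claim is that device use is not listed in the protocol. It would be wrong to say that it could never be recovered.

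**Extension to the primary endpoint.** A reader might infer that MMTTs done under a different background insulin could not be identified, so that the C-peptide AUC is also affected. The document does not support this. Study procedure sets one background-insulin condition for all MMTTs, and Ethics and dissemination says that protocol deviations will be monitored and noted. A test done under another condition is therefore already meant to be identified. Routine device use between tests breaches no stated rule and would not be caught that way.

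**Partial remedy.** Devices are one of many possible correlates of family motivation, and two fields leave the others unmeasured. This stands. Device use is nonetheless a specific co-intervention that is cheap to record.

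**Conclusion.** The point holds for HbA1c, insulin requirement and IDAA1c, and for nothing beyond them. With free choice of arm and no listed device variable, the planned analyses would attribute any between-arm difference in device use to diet.

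The size is unknown. It depends on the uptake gap, which may be zero or of either sign; the upper end of the illustrated range requires a 40-point gap, a 0.5 SD effect and 50 children per arm together. This is a sensible improvement to make and does not invalidate the trial.

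**What to change.** 1. **Record.** Add two fields to the allocation form and to every 3-monthly visit form: insulin delivery (injections or pump) and glucose sensor (yes or no), each with a start date. Fill visits already completed from the diabetes clinic record.
2. **Report.** Tabulate both by arm at each visit, with use at allocation shown separately from later uptake.
3. **Analyse.** For HbA1c, insulin requirement and IDAA1c, add an analysis adjusted for device use at allocation, and a clearly labelled sensitivity analysis that includes device use during follow-up.

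The cost is two form fields, a retrospective chart check, one table and two extra model runs per endpoint.

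The downside is that device use started after allocation is post-baseline and may partly follow from arm, for instance through the extra contact in the diet group. The follow-up model is therefore supportive only. The baseline-adjusted model avoids that difficulty but removes little if most devices are started later, which is why the by-arm table matters most. Nothing here changes care or recommends any device or regimen.

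### The primary 12-month ANCOVA has no missing-data method and cannot use a child who has only a 6-month AUC, so selective loss that differs between arms would bias the diet effect

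*Combined protocol and SAP*

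**What the plan says.** All references are to the combined protocol and SAP.

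- **End points:** the primary endpoint is "Area under the curve (AUC) of the C-peptide level during the mixed meal tolerance tests".
- **Study procedure, schedule:** "MMTTs will be performed for all subjects at group allocation and at 6 and 12 months". A child can therefore have a 6-month AUC and no 12-month AUC.
- **Statistical analysis, primary model:** an ANCOVA "with C-peptide AUC at 12 months as a response", with the chosen arm and "baseline C-peptide AUC at visit 1, age, gender and body weight as covariates". The 6-month AUC is neither a response nor a covariate. Inference uses a sandwich variance, and the analysis is per-protocol, a term the document does not define.
- **Statistical analysis, 6 months:** "Secondly, the results at 6 months will also be analyzed".
- **Statistical analysis, longitudinal:** linear GEE models with working independence compare 12-month trends between arms. They are not the primary analysis and are not offered as a way to handle missing AUCs.
- **Participants, withdrawal:** "Subjects and their parents have the right to withdraw from the study at any time without giving the reason".
- **Study procedure, allocation:** "The subjects and their parents will choose their study group freely".

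The document gives no imputation rule, no likelihood-based repeated-measures model, no missing-data sensitivity analysis, and no sample size, SD or expected dropout.

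**The concern.** An ANCOVA with one response at one time point can be fitted only to children who have that response. Those left out may include children whose 6-month AUC shows how they were doing.

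The design allows such loss to differ between arms. Families know their arm because they chose it, and only the diet arm carries the strict diet and its adherence testing. A 12-month AUC can also be missing without withdrawal: the Study procedure section reschedules a test when glucose is out of range, but does not say what happens if no valid test follows. The undefined per-protocol rule adds a further route, since a child who stops the diet may be excluded despite attending the 12-month test.

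If diet-arm children with low 6-month C-peptide are the ones lost, those who remain overstate preserved beta-cell function, and the primary result is the one affected.

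**Working it through.** The plan gives no figure to reproduce. Every input below is an assumption.

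**Inputs.** True diet effect 0. Residuals of the 6- and 12-month AUC, given baseline, have SD 1 and correlation ρ. Only the diet arm loses 12-month values. The log-odds of loss rise by s for each SD that the 6-month residual e₆ falls. The overall loss in that arm is d.

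**Bias of the planned ANCOVA.** Let m be the mean of e₆ among diet-arm children who stay:

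m = ∫ e φ(e) [1 − p(e)] de / (1 − d), where p(e) = 1 / (1 + exp(−a + s·e)) and a is set so that the average of p is d.

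Given e₆, loss does not depend on the 12-month residual. The diet-arm mean at 12 months is therefore shifted by ρ·m, and

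bias = ρ × (m in diet arm − m in control arm).

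With no loss in the control arm its m is 0. The simulated column comes from 2,000 trials per setting with 30 children per arm.

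| Loss d | m (s = 1) | Bias, ρ = 0.5 to 0.8 | m (s = 1.5) | Bias, ρ = 0.4 to 0.8 | Simulated, s = 1.5, ρ = 0.4 to 0.8 |
|---|---|---|---|---|---|
| 10% | 0.091 | 0.05 to 0.07 | 0.122 | 0.05 to 0.10 | 0.05 to 0.10 |
| 20% | 0.173 | 0.09 to 0.14 | 0.227 | 0.09 to 0.18 | 0.08 to 0.18 |
| 30% | 0.253 | 0.13 to 0.20 | 0.327 | 0.13 to 0.26 | 0.13 to 0.26 |

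Example: 0.8 × 0.227 = 0.18 SD. The formula and the simulation agree. Results at 20 per arm were similar, because the bias hardly depends on sample size.

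**When the bias vanishes.** If both arms lose equally selectively, the two m terms cancel. If loss is random, m = 0. Simulated at 20% loss, 30 per arm and ρ = 0.6, the bias was 0.002 and 0.001.

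**Effect on the test.** At 30 per arm, with no loss, the standard error is about √(1/30 + 1/30) = 0.26 SD. A bias of 0.05 to 0.2 SD is then about 0.2 to 0.8 of a standard error. In simulation with ρ = 0.8 and s = 1.5, the nominal 5% two-sided test rejected in 11% of trials at 20% loss and 17% at 30%. A run with no loss gave 5.5%.

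**The planned GEE.** A linear-trend GEE with working independence was biased by 0.07 to 0.17 SD at 20% loss and 0.11 to 0.24 SD at 30%. It uses the 6-month value but does not carry its correlation with the 12-month value into the estimate.

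**Joint model of 6 and 12 months.** This estimates the 6-month arm difference from all children and the regression of the 12-month on the 6-month AUC from completers, and combines the two. Its mean estimate lay between −0.01 and +0.02 SD in every setting above.

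**Where the joint model falls short.** If loss depends on the unseen 12-month value (s = 1), the large-sample biases are:

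| Loss | ANCOVA | Joint, ρ = 0.5 | Joint, ρ = 0.8 |
|---|---|---|---|
| 10% | 0.09 | 0.07 | 0.03 |
| 18% | 0.16 | 0.12 | 0.06 |
| 30% | 0.25 | 0.19 | 0.09 |

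If half of the leavers go before the 6-month test (18% loss, ρ = 0.8, s = 1, 30 per arm), the ANCOVA bias is 0.12 SD and the joint-model bias 0.06 SD.

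**The case against.** **Selective loss is assumed, not shown.** A reader might infer from the burden of the diet and the right to withdraw that children doing badly will probably leave the diet arm. The documents do not support that. They give no rate, reason or direction, and the Intervention section reimburses the added cost of gluten-free food, which works against loss. If children doing well left instead, the sign would reverse. This stands: the bias is conditional.

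**The plan never says that such children are dropped.** True. It follows from a single-time-point model with no missing-data method.

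**A longitudinal analysis is planned.** Also true, and it would be wrong to infer that the 6-month AUC is never analysed. But that analysis is secondary, and its working-independence form leaves most of the bias in place.

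**The per-protocol rule is the larger exclusion.** Leaving the diet is not the same as lacking a 12-month AUC, and a joint model confined to per-protocol children would not bring back those already excluded. This stands, and it is why the fix must name the analysis set.

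**The correction is oversold.** A reader might infer that the 6-month AUC removes most of any bias. That holds only under missingness at random; the last table shows how little may be removed otherwise. Nor is precision a reason to change: in the simulations the standard error moved by only 1 to 3%.

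**Confounding from free choice of arm may matter more.** Possibly, but it is a separate problem, and neither model solves it.

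**Conclusion.** The concern holds in conditional form. As written, the primary estimate ignores the 6-month AUC of any child without a usable 12-month AUC, and no other planned analysis repairs this. If loss is both selective and different between arms, the diet effect is biased. With 10 to 30% diet-arm loss driven by low 6-month AUC, the bias is about 0.05 to 0.2 SD towards the diet, reaching 0.26 SD at the steepest dependence and highest correlation tried. With random or equally selective loss it is about zero.

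The direction under these conditions follows from the model. The size rests on the assumed loss, correlation and steepness. The documents support neither a claim that the result will be biased nor a claim that a joint model would remove the bias whatever the cause of loss.

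**What to change.** 1. **Primary model.** Fit one repeated-measures model to the 6- and 12-month AUC, with arm, baseline AUC, age, sex and body weight each interacting with visit and an unstructured 2×2 covariance. Keep the planned robust variance, with a small-sample correction. The primary contrast is the arm difference at 12 months; the same model gives the 6-month result. With no AUC missing, both visits share the same regressors, so the 12-month estimate equals that of the planned ANCOVA.
2. **Analysis set.** State it as every child with a baseline and at least one later MMTT, by chosen arm. This changes the population from the present per-protocol wording and should be declared as such. Define per-protocol; any per-protocol version should keep the MMTTs obtained before the child left the protocol instead of removing the child.
3. **Sensitivity analyses.** Keep the complete-case ANCOVA. Add a missing-not-at-random analysis that shifts the imputed 12-month AUC of children with missing values by a range of deltas. For scale, a shift of 0.5 SD in 20% of one arm moves the contrast by 0.2 × 0.5 = 0.1 SD.
4. **Reporting.** Give the number of missing 12-month AUCs by arm, with reasons where known and the 6-month AUC of those children.

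**Cost.** SAP wording and slightly more analysis work; no new data. The new primary analysis relies on missingness at random given the 6-month AUC, and corrects only partly if loss depends on the unseen 12-month value or occurs before month 6.

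### Does leaving the sandwich variance variant unnamed put the primary test's error rate at risk?

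*Combined protocol and SAP*

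**What the plan says.** The primary analysis is an ANCOVA of 12-month C-peptide AUC with "the intervention assignment, baseline C-peptide AUC at visit 1, age, gender and body weight as covariates". On inference the Statistical analysis section has one sentence: "The tests and confidence intervals will use robust sandwich variance estimator". It then states "The primary analysis will follow the per-protocol principle". The 6-month and secondary outcomes are to be analysed along similar lines. For trends over time it says "Longitudinal analyses will be performed by linear generalized estimating equation models with a working independence structure", with slopes that "over 12 months will be estimated by the intervention arm and compared with adjustment for sex, age, and baseline body weight SDS".

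No sample size, significance level or expected arm split appears. The Participants section says the centres "annually admit over 65 children patients with newly diagnosed T1D" and "The recruitment will last from January 2016 to January 2018". Under Study procedure, "The subjects and their parents will choose their study group freely", so the split between arms is not controlled.

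**The concern.** The sandwich estimators called HC0, HC1, HC2 and HC3 agree only in large samples. HC0 uses squared residuals as they stand. These are too small on average, because the fitted model has absorbed part of the error, so HC0 understates the standard error when the number of children is not large relative to the six coefficients. A normal rather than a t reference makes the understatement worse.

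The plan does not exclude that combination, and a small analysed number is plausible. Antibody, HLA, BMI and coeliac criteria, consent to a trial with a strict diet arm, and per-protocol exclusions all reduce the pool. If HC0 with normal critical values were applied to 30 to 40 children, the false-positive rate would be roughly 1.6 to 2.2 times nominal (8.1/5 to 10.8/5), and an unstated software option would move the confidence limits.

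**Working it through.** **Inputs from the document.** There are six coefficients: intercept, arm, baseline AUC, age, gender and weight. Recruitment lasts two years. If the figure of over 65 a year covers both centres together, the pool is at least 2 × 65 = 130 diagnoses; if it is per centre, at least 2 × 130 = 260. Both counts precede eligibility, consent and per-protocol losses.

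**Assumptions.** Two-sided 5% level; analysed n from 30 to 260; all covariate and error distributions. The document gives none of these and no operating figure to reproduce.

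**Approximate check.** If the average standard error is a fraction r of the true one, the rejection rate with normal critical values is about 2 × [1 − Φ(1.96 r)]. Simulated r for HC0 was 0.84–0.87 at n=30, 0.88–0.91 at n=40 and 0.91–0.94 at n=60. The formula gives 8.8–10.0%, 7.5–8.5% and 6.5–7.5%. The full simulation runs somewhat higher because the standard error also varies from sample to sample.

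**Simulation.** 10,000 null trials per cell, eight cells at each n. Baseline AUC was skewed, age ran from 4 to 18, weight was correlated with age, and 33% or 50% were on the diet. Errors were normal, skewed, rising with baseline AUC, or with 1.5-fold SD in the diet arm. The last column is exact: HC1 is HC0 multiplied by √(n/(n−6)), so the interval ratio is √(n/(n−6)) × t(n−6)/1.960. At n=30 this is 1.118 × 2.064/1.960 = 1.177.

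| n | HC0, normal reference: null rejection | HC2 with t: extra interval width over HC0-normal | HC1 with t: extra width |
|---|---|---|---|
| 30 | 9.5–10.8% | 19–21% | 17.7% |
| 40 | 8.1–9.4% | 13–15% | 12.5% |
| 60 | 6.6–8.4% | 8–9% | 7.8% |
| 100 | 5.5–6.8% | 4–5% | 4.5% |
| 130 | 5.8–6.4% | 4–5% | 3.4% |
| 260 | 5.3–5.8% | 2% | 1.7% |

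A separate simulation (20,000 trials per scenario) gave 9.3–11.1% at n=30 and 7.8–9.5% at n=40 for HC0 with a normal reference, leaving out unequal arm SDs. A further run, with SD ratios up to 1.5, reached 12.0% at n=30. With a 2:1 SD ratio between arms the ranges were 9.0–14.2% and 7.4–11.3%. HC0 with t(n−6) gave 7.8–9.5% and 6.7–8.5%, again without unequal SDs.

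**Other readings of the same sentence, n=30–40.** In the table's simulation: HC1 with t, 5.0–6.4%; HC2 with t, 4.8–6.2%; HC3 with normal reference, 3.5–4.9%; HC3 with t, 2.8–4.2%.

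**Is one corrected form clearly best?** With twice the SD in the smaller arm and a 67:33 to 75:25 split, HC2 with t(n−6) ran at 6.6–8.2% at n=30–40, and HC3 with t at 4.4–5.0%. In milder settings the order reverses: HC2 with t is close to 5% and HC3 with t is conservative.

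**GEE slopes.** An uncorrected sandwich clustered on child, with a normal reference, gave 6.7–8.2% at n=30, 5.8–6.9% at n=40 and 5.5–6.2% at n=60. At n=100–130 no clear inflation could be resolved (4.6–7.1%, Monte Carlo SE about 0.6 points). That simulation used five quarterly visits. This matches HbA1c and insulin dose, but C-peptide and the immune markers are measured only at baseline, 6 and 12 months.

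**The case for a change.** The strongest case for a change is that prespecification exists to remove this kind of discretion. The gap is real, the inflation under the worst reading was reproduced in separate simulations, and the remedy costs one or two sentences. A small per-protocol set cannot be ruled out, and families choosing their own group could produce an unbalanced split. The primary limits could then move by 13 to 21% at n=30–40 according to a software option.

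The gap and the arithmetic stand. What does not follow is that the plan is wrong as written:

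- The inflated figure needs three unstated things together: HC0, normal critical values and 30 to 40 children. Falling to that size from 130 diagnoses means losing 69 to 77% (1 − 40/130 and 1 − 30/130). The document neither supports nor excludes that.
- An analyst facing a small sample who reads the sentence can apply a corrected form with a t reference without departing from it.
- Prescribing one form would replace an open choice with a contestable one. HC2 with t loses control in the very setting that best justifies a robust estimator, a small and more variable arm. HC3 with t gives up precision elsewhere.
- The GEE sentence names no variance estimator, but it sits in the paragraph that adopts the sandwich for tests and intervals. A robust variance clustered on child is the natural companion of working independence. A compulsory small-sample correction for secondary trend analyses would be out of proportion to the inflation seen.

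**Conclusion.** The concern does not call for a change. The plan commits to a robust variance, which is a sound choice: with 1.5 times the error SD in a 33% arm, ordinary least squares with t rejected 7.3–8.4%. What it leaves open is a technical setting that a competent analyst fixes when the analysis is programmed and reports with the results.

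At 100 or more analysed children the worst reading costs about half a point to two points of type I error (5.5–6.8% against 5%). At 30 to 40 it costs roughly 3 to 7 points, but only if HC0 is paired with normal critical values; the corrected forms mostly show little inflation or are mildly conservative. These sizes rest on an assumed two-sided 5% level, assumed analysed numbers and assumed distributions.

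The missing sample size and significance level are separate omissions. Bias from self-chosen groups and from the per-protocol set matters more than the variance form, and no sandwich variant corrects it.
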